1.0 Study Summary

Study Title	Weight management program for patients with first episode psychosis.
Study Design	This is a multiple baseline N of 1 intervention with 12 individuals
Primary Objective	Determine the feasibility, acceptability, and effect of a weight management program for patients prescribed antipsychotic medications for a first episode of psychosis.
Secondary Objective(s)	
Research Intervention(s)/ Investigational Agent(s)	Three month weight management program
IND/IDE #	
Study Population	Adults and adolescents participating in treatment through the NAVIGATE program for an initial episode of psychosis and one of their parents or a household family member (e.g., parent, guardian, grandparent, aunt or uncle).
Sample Size	12 patients and 12 family members
Study Duration for individual participants	Up to 9 months

Study Specific Abbreviations/ Definitions	Severe mental illness (SMI)
--	-----------------------------

2.0 Objectives*

2.1 *Describe the purpose, specific aims, or objectives of this research.*

Response: This pilot study will determine the acceptability and potential value of a family-oriented weight management program for individuals receiving anti-psychotic medication for a first episode of psychosis.

2.2 *State the hypotheses to be tested, if applicable.*

NOTE: A hypothesis is a specific, testable prediction about what you expect to happen in your study that corresponds with your above listed objectives.

Response: Patients will lose weight after treatment is initiated in comparison to the two month baseline during which they simply weigh themselves daily.

3.0 Scientific Endpoints*

3.1 *Describe the scientific endpoint(s), the main result or occurrence under study.*

*NOTE: Scientific endpoints are outcomes defined before the study begins to determine whether the objectives of the study have been met and to draw conclusions from the data. Include primary and secondary endpoints. Some example endpoints are: reduction of symptoms, improvement in quality of life, or survival. Your response should **not** be a date.*

Response: The primary endpoint will be the participants' weights. Secondary endpoints will be participation in the weekly interventions and the percent of daily weight reports.

4.0 Background*

4.1 *Provide the scientific or scholarly background, rationale, and significance of the research based on the existing literature and how it will contribute to existing knowledge. Describe any gaps in current knowledge. Include relevant preliminary findings or prior research by the investigator.*

Response: Severe mental illness (SMI), such as schizophrenia and bipolar disorder, are associated with increased morbidity and mortality from somatic disorders. People with a severe mental illness have a life expectancy as much as 10-20 years less than people without such disorders (Lomholt, et al, 2019). These differences in morbidity are reflected in healthcare costs, with SMI patients incurring nearly \$5,000 in annual Medicare costs for physical conditions more than patients without

SMI with excesses observed for diabetes as well as ischemia and congestive heart failure. (Figueroa, et al 2020).

While there are a number of factors that contribute to the physical health risks of people with SMI, obesity is of particular importance. Obesity creates an increased risk for many common medical conditions, such as diabetes, heart disease, hypertension and cancer. Moreover, people with SMI are about twice as likely as those without to be obese (McElroy, 2009). While there has been some evidence that suggests that individuals with SMI may be predisposed toward obesity and metabolic dysfunctions, it is also clear that psychosocial factors and antipsychotic medications have a very strong impact.

Among the psychosocial factors that appear to play a role are low self-efficacy and motivation for physical/social activities, effects that may be exacerbated with the stigma experienced from the disorder, as well as from the effects of medications to treat SMI (Gates, Killackey, Philips, & Alvarez-Jimenez, 2015).

Antipsychotic medications also are powerful contributors to weight gain. D'Aurignac, [name], and Dubovsky (2014) demonstrated that olanzapine, but not a placebo, led to a significant weight gain of 3.74 lbs. among healthy participants in only two weeks. Moreover, while not all subjects who received olanzapine gained weight, subjects who gained weight on olanzapine gained an average of 5.28 lbs., and also experienced increases in LDL cholesterol, insulin, and leptin. Among adults with a first-episode psychosis, olanzapine resulted in an increase of 10.34 lbs. in 12 weeks, and increases in insulin, c-peptides and triglycerides (Graham et al, 2005). This increase in weight, as well as increases in cholesterol, leptin, and insulin, continue to increase over the first year of antipsychotics, and then stabilize (Mustafa, et al, 2019; Perez-Iglesias et al, 2014).

There have been numerous studies that have examined weight loss interventions among those with SMI. One of the most well-known, ACHIEVE, compared an 18 month lifestyle intervention (diet and exercise) with a control condition for SMI patients attending day treatment centers. At the end of the 18 months, patients who received the lifestyle intervention had lost 7.5 lbs., in contrast to less than .50 lbs. in the control. Aside from this lengthy and intensive intervention, most studies have not demonstrated this large of an effect. A recent meta-analysis examined 41 randomized clinical trials focusing on interventions that attempted to decrease body weight through improved diet, increased activity, or both (Speyer, et al, 2019). The overall conclusion was that

these interventions led to statistically significant weight loss that was of no clinical significance (a difference of approximately 4.8 lbs), and which did not persist beyond the intervention. While neither this meta-analysis nor an earlier one (Alvarez-Jimenez, Hetrick, Gonzalez-Blanch, Gleeson, & McGorry, 2008) found that the effects were stronger for patients with a shorter duration of disorder, studies of weight management in other samples often find that it is easier to prevent weight gain than to lose weight, given metabolic changes that occur with increased weight. As a result, there has been recent interest in interventions to prevent weight gain among patients experiencing their first episode of SMI.

While there has been interest in developing effective early interventions for patients experiencing their first episode of a SMI, most of the work has attempted to establish the acceptability and feasibility of interventions (e.g. Thompson, et al, 2020), or has conducted small, uncontrolled studies of changes in weight in a group receiving the intervention. There have been very few randomized clinical trials. For example, Curtis et al (2016) provided 26 patients with a 12 week lifestyle and life skills intervention and 23 patients with standard care. Only 57% completed the programs and were available for analyses. At the end of the 12 weeks, the intervention group, which contained three times as many women as standard care, only gained 4.0 lbs, while the standard care group gained 17 lbs. The largest and most well-controlled study to date was conducted by Alvarez-Jimenez and colleagues (Alvarez-Jimenez et al, 2006; Alvarez-Jimenez et al, 2010). This study randomized 28 patients to a 7-16 session early behavioral treatment including psychoeducation, dietary counseling, exercise, and behavioral therapy and 33 patients to routine care. Patients in the behavioral treatment had gained significantly less weight, 9.0 lbs, by the end of the 3 month program than patients in routine care gain, 15.2 lbs. Nearly 97% of the sample was successfully followed up one year later, and there were not differences in their weight.

Given the poor adherence in one study and the lack of a lasting effect, modifications of these weight management programs would be important to consider. One particular aspect that has been shown to be effective with adolescents is the involvement of a parent.

4.2 Include complete citations or references.

Response: Alvarez-Jimenez, M., Gonzalez-Blanch, C., Vazquez-Barquero, J.L., Perez-Iglesias, R., Martinez-Garcia, O., Perez-Pardal, T., Ramirez-Bonilla, M.L., & Crespo-Facorro, B. (2006). Attenuation of antipsychotic-induced weight gain with early behavioral intervention in drug-naive first-

episode psychosis patients: A randomized controlled trial. *Journal of Clinical Psychiatry*, 67(8), 1253-1260.

5.0 Study Design*

5.1 *Describe and explain the study design (e.g. case-control, cross-sectional, ethnographic, experimental, interventional, longitudinal, observational).*

Response: This is a multiple baseline N of 1 design. Participants will chart their weight for two months prior to the initiation of a weight management program, and continue to chart their weight throughout the 3 month intervention and for 2 months following the intervention.

6.0 Study Intervention/Investigational Agent

6.1 Describe the study intervention and/or investigational agent (e.g., drug, device) that is being evaluated.

Response: Families will receive a 12-week FBT adapted for first episode psychosis. This will be delivered in 12 weekly meetings with a trained case manager and two “eating plan” education sessions. Both the patient with psychosis and parents are targeted for eating and activity/exercise change to ensure a change in the shared family environment, which will also help weight control in both sets of participants, as well as medical issues that accompany obesity, including glycemic control, hypertension and hyperlipidemia. If parents are not overweight/obese, they will still target improved health behaviors. They will learn about GREEN, YELLOW, and RED foods (healthy vs. unhealthy foods), energy density, glycemic index of foods, reducing serving sizes, eating less, healthy lifestyle and programmed activity programs and recording their diets and activity.

Weekly sessions will involve discussion of weight loss principles presented in modules in the weight control manual, and coaching parents and patients how to implement the Traffic Light Eating Plan and healthy lifestyle techniques. At each session, participants meet with staff and attend a brief problem solving session with their case manager where they will troubleshoot any expected or encountered issues with implementing the program. This intervention may be through Zoom (which is still approved for telemedicine interventions in New York) or in-person. The NAVIGATE program has used telemedicine with this patient group throughout the past year successfully. As part of treatment, participants will weigh themselves daily with a Bluetooth scale. Contingency management (\$1 per completed weighing) will be used to facilitate adherence to this weighing schedule.

An innovative aspect of this treatment is helping patients develop alternative reinforcements that do not involve food that can reduce the motivation to eat for the hedonic or reinforcing motivations. The first step is to identify alternative activities that have a higher reinforcement value than the patients’ favorite foods. First, participants will identify potential alternatives from the 139 behaviors on the Pleasant Activities List. The therapist then works with the patient to better specify the behavior, ensure its feasibility and describe the parameters of the behavior (e.g. duration). After the participant and case manager agree on a list of alternatives (at least 5), the participant will complete the Behavioral Choice Questionnaire that assesses the reinforcing value of that activity in comparison to food. The most reinforcing food to be used to assess behavioral substitutes will be chosen from a list of usual meals that can be obtained from home cooked, fast food or casual dining restaurants. These alternative reinforcements are used non-contingently by the patients/parents to provide highly desirable activities that compete with excessive food consumption.

6.2 Drug/Device Handling: If the research involves drugs or device, describe your plans to store, handle, and administer those

drugs or devices so that they will be used only on subjects and be used only by authorized investigators.

- *If the control of the drugs or devices used in this protocol will be accomplished by following an established, approved organizational SOP (e.g., Research Pharmacy SOP for the Control of Investigational Drugs, etc.), please reference that SOP in this section.*

Response: NA, the medication that patients are taking will be managed by their physician and only be a screening criteria.

6.3 *If the drug is investigational (has an IND) or the device has an IDE or a claim of abbreviated IDE (non-significant risk device), include the following information:*

- *Identify the holder of the IND/IDE/Abbreviated IDE.*
- *Explain procedures followed to comply with sponsor requirements for FDA regulated research for the following:*

FDA Regulation	Applicable to:		
	IND Studies	IDE studies	Abbreviated IDE studies
21 CFR 11	X	X	
21 CFR 54	X	X	
21 CFR 210	X		
21 CFR 211	X		
21 CFR 312	X		
21 CFR 812		X	X
21 CFR 820		X	

Response: NA

7.0 Local Number of Subjects

7.1 *Indicate the total number of subjects that will be enrolled or records that will be reviewed locally.*

Response: 30 participants, made of 15 patient and family member dyads, will be enrolled. Each one of the participants must have a household family member willing to collaborate in the program.

7.2 *If applicable, indicate how many subjects you expect to screen to reach your target sample (i.e. your screen failure rate).*

Response: We expect to screen approximately 50-75 individual patients in order to recruit 12 patient and family member dyads who complete 75% of their visits.

We are planning to enroll 15 dyads, but anticipate that 3 will not complete 75% of their visits.

7.3 *Justify the feasibility of recruiting the proposed number of eligible subjects within the anticipated recruitment period. For example, how many potential subjects do you have access to? What percentage of those potential subjects do you need to recruit?*

Response: The NAVIGATE program admits 2 to 3 patients per month. At the beginning of the study, we anticipate that there would be approximately 40-45 patients in the program with the requisite use of antipsychotic medications, and over the next five months, we would expect an additional 10-15 patients. Assuming that 50% of the patients are eligible and interested, we would have approximately 25-30 patients available for the study.

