12.0 Study Timelines*

12.1 Describe the anticipated duration needed to enroll all study subjects.

Response: We expect to enroll all study subjects within 6 months.

12.2 Describe the duration of an individual subject's participation in the study. Include length of study visits, and overall study follow-up time.

Response: Participants will be involved in the study for a total of up to 9 months. They will have 3 in person assessments, and 12 weekly interventions via zoom or or in person. The assessments and the weekly interventions will take approximately 1 hour.

While we expect participation to be completed in 7 months (2 months baseline, 3 months treatment, 2 months follow-up), we are allowing extra time for the rescheduling of missed appointments, etc.

12.3 Describe the estimated duration for the investigators to complete this study (i.e. all data is collected and all analyses have been completed).

Response: We expect to be able to complete the analyses within 6 months of the final follow-up assessment.

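### Do the two adherence endpoints need a written denominator, and does the 12 in the study summary conflict with the 15 dyads enrolled?

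*Combined protocol and SAP*

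**What the plan says.** **Sample size.** The study summary (section 1.0) describes the design with "This is a multiple baseline N of 1 intervention with 12 individuals" and gives the sample size as "12 patients and 12 family members". Section 7.1 states "30 participants, made of 15 patient and family member dyads, will be enrolled". Section 7.2 plans its screening "in order to recruit 12 patient and family member dyads who complete 75% of their visits" and connects the two figures: "We are planning to enroll 15 dyads, but anticipate that 3 will not complete 75% of their visits".

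**Adherence endpoints.** Section 3.1 makes weight the primary endpoint and adds: "Secondary endpoints will be participation in the weekly interventions and the percent of daily weight reports". It states no denominator. On the schedule, section 6.1 says "This will be delivered in 12 weekly meetings with a trained case manager and two" education sessions, and section 12.2 says "They will have 3 in person assessments, and 12 weekly interventions via zoom" or face to face. Section 17.1 counts 60 baseline, 90 treatment and 60 follow-up days of weights. The compensation section pays $1 per day with a weight, up to $210 per person.

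**Analysis and withdrawal.** Section 17.1 fits a separate model of daily weight for each participant. It defines no pooled estimate and no analysis of the two adherence endpoints. Section 20.1 removes a patient who leaves the clinical program or has a long relapse admission, and lets the relative carry on. Section 20.3 keeps the data of everyone who withdraws, whether before or after the halfway point of the program.

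**The concern.** A percentage means little until its denominator is known, and feasibility and acceptability are part of the primary objective in section 1.0. If attendance were averaged only over dyads that reached 75% of visits, the result would be high by construction. If a removed patient were counted only while in the study, early loss would not show in the reporting percentage. Because section 20.1 lets the relative stay on, the two members of a dyad can have different numbers of observed days, and the plan does not say whether to count them separately. Section 11.4 also allows clinic weights to be taken from the medical record when someone does not weigh in, and these might be mistaken for daily reports. Finally, a reader of section 1.0 alone would take 12 as the enrolment figure and could suspect that three dyads are to be dropped.

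**Working it through.** **1. The plan's own figure.** Inputs from sections 7.1 and 7.2: 15 dyads enrolled, 3 expected to fall short.
- 15 − 3 = 12 completers, and 3/15 = 20%.
- In reverse, 12 / (1 − 0.20) = 15 dyads, and 2 × 15 = 30 people.

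Sections 7.1 and 7.2 agree and explain the 12 in section 1.0. No analysis uses the summary's figure.

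**2. Denominators that can be read from the plan.**
- Weekly sessions: 12 (sections 6.1 and 12.2).
- Weighing days: 60 + 90 + 60 = 210 (section 17.1), which matches the $210 cap at $1 per day.
- Section 17.1 also gives a calendar. The earliest starter begins baseline in week 1 and treatment in week 9, finishes treatment in week 21 and ends follow-up in week 29. That is 8 + 12 + 8 = 28 weeks, or 196 days.

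The 210 and the 196 both look like roundings of 2 + 3 + 2 = 7 months. Someone who weighs in every day on the 28-week calendar would score 196/210 = 93.3%. A single fixed number is therefore no more accurate than each person's dated schedule.

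**3. Completers against all enrolled.** Read visits as the 12 weekly sessions. The 75% mark is then 9 sessions, so the 12 completers attend 9 to 12 and the other 3 attend 0 to 8. The planned total is 15 × 12 = 180 dyad-sessions.
- Completers alone: 75% to 100%.
- All 15, lowest: (12 × 9 + 3 × 0)/180 = 60.0%.
- All 15, highest: (12 × 12 + 3 × 8)/180 = 93.3%.
- Gap = (3/15) × (completer rate − non-completer rate). Smallest: 0.2 × (9/12 − 8/12) = 1.7 points. Largest: 0.2 × (1 − 0) = 20 points.

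The gap arises only if someone reports completers alone. No section calls for that, and section 20.3 points the other way by keeping all data.

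**4. A removed patient.** Compare planned days with days in the study, assuming full reporting while in the study. Each removal at day d changes the percentage by (210 − d) over the planned total, which is 15 × 210 = 3150 patient-days, or 30 × 210 = 6300 person-days with relatives pooled in.

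| Removed at day | Patients only | Pooled with relatives who all continue |
|---|---|---|
| 60 | 150/3150 = 4.8 points | 150/6300 = 2.4 points |
| 105 | 105/3150 = 3.3 points | 105/6300 = 1.7 points |
| 150 | 60/3150 = 1.9 points | 60/6300 = 1.0 point |

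With a reporting rate p while in the study, each figure is multiplied by p. The removal days are assumed, since the plan forecasts no removals. The 3 dyads in section 7.2 miss visits and need not withdraw.

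**5. Clinic weights.** Section 11.2 defines the daily weight as one taken on the supplied Bluetooth scale, and section 18.4 has it collected by an app. Section 11.4 turns to clinic weights only for someone who is not weighing in. A clinic weight therefore marks a missing daily report and is not itself a daily report.

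**The case for a change.** The strongest argument for a change is that adherence is much of the reason for this pilot. Section 4.1 cites an earlier trial in which only 57% completed and were available for analysis, and uses poor adherence to justify a modified program. Such a study could be expected to say in advance how adherence is counted. Session and day totals can be inferred, but the treatment of days after removal cannot, nor can separate or joint counting of patient and relative. Section 20.3 uses 50% of the program as its marker while section 7.2 uses 75% of visits. The word visit itself has four readings: 9 of 12 weekly sessions, 11 of 14 with the education sessions, 12 of 15 with the assessments, or 13 of 17 with both. Settling all this would cost a few sentences.

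Some of this stands. The plan is silent on days after removal and on separate counting, and its day count and calendar do not match exactly. What fails is the step from silence to a wrong result. The 75% mark in section 7.2 is a recruitment allowance and the 50% mark in section 20.3 concerns retention of data; neither is an analysis set. Writing in 210 days would also be no clear gain: on the 28-week calendar it takes 6.7 points from a fully adherent participant, more than the largest removal effect in the table.

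**Conclusion.** No change is needed. The 12 in section 1.0 is a clerical omission that sections 7.1 and 7.2 resolve. The missing denominators are a gap that analysts would ordinarily fill sensibly: report all 15 dyads, show patients and relatives separately, and print the denominator beside each percentage. With 15 dyads, attendance and reporting can also be listed person by person, which would leave little for a denominator choice to hide.

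The primary weight analysis is unaffected, because each participant has a separate model. The remaining effect is confined to two secondary descriptive percentages. It is at most 4.8 points per patient removed at day 60 and less for later removals, assuming 210 planned days and full reporting before removal. The 1.7 to 20 point gap is not an effect of the plan, since no completer-only summary is planned. This conclusion rests on section 20.3 being followed, so that the data of early leavers are kept and remain available to every summary.

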8.0 Inclusion and Exclusion Criteria*

8.1 *Describe the criteria that define who will be **included** in your final study sample.*

NOTE: This may be done in bullet point fashion.

Response:

Participant:

-Age 14-26 years

-Enrolled in NAVIGATE, a clinical program for patients with first episode of psychosis.

-Prescribed antipsychotic medication for a first break psychotic episode

-Availability of household family member to collaborate in the weight management program.

Family Member:

-Lives in the same household as participant (e.g., parent, guardian, grandparent, aunt or uncle)

-Able to attend weekly meetings with a case manager

8.2 *Describe the criteria that define who will be **excluded** from your final study sample.*

NOTE: This may be done in bullet point fashion.

Response:

Participant & Family Member:

-Personal or Family history or evidence of current eating disorders (bulimia or anorexia or binge eating disorder)

- Current alcohol or drug abuse,
- Unable to read at 8th grade level
- Unable to use technology.
- Unable to weigh themselves daily due to existing medical condition
- Pregnant or planning on becoming pregnant during the study

8.3 *Indicate specifically whether you will include any of the following special populations in your study using the checkboxes below.*

NOTE: Members of special populations may not be targeted for enrollment in your study unless you indicate this in your inclusion criteria.

Response:

- Adults unable to consent
- Individuals who are not yet adults (infants, children, teenagers)
- Pregnant women
- Prisoners

8.4 *Indicate whether you will include non-English speaking individuals in your study. Provide justification if you will exclude non-English speaking individuals.*

*In order to meet one of the primary ethical principles of equitable selection of subjects, non-English speaking individuals may **not** be routinely excluded from research as a matter of convenience.*

In cases where the research is of therapeutic intent or is designed to investigate areas that would necessarily require certain populations who may not speak English, the researcher is required to make efforts to recruit and include non-English speaking individuals. However, there are studies in which it would be reasonable to limit subjects to those who speak English. Some examples include pilot studies, small unfunded studies with validated instruments not available in other languages, studies with numerous questionnaires, and some non-therapeutic studies which offer no direct benefit.

Response:

Participants must be able to read English at 8th grade level in order to complete questionnaires. English version surveys and complex instructions make enrolling non-English speakers impractical within this budget.

